108 awareness of HIV status, reduce injection-related and same-sex risk behavior, improve health,

109 reduce mortality, and decrease the infectiousness of HIV-infected persons in the community
110 through effective viral suppression. We will evaluate the community-level effectiveness of
111 MSM//PWID-focused integrated care centers (ICCs), which will provide core and group-specific
112 HIV prevention and treatment services at a single venue utilizing a cluster-randomized trial
113 design in 22 sites across India.

114

115 Our hypotheses are:

116 1) Establishing ICCs will increase access to HCT and knowledge of HIV status among MSM and
117 PWID.

118 2) In the subset of HIV-infected MSM and PWID, ICCs will increase access to care, use of ART
119 and will decrease community viral load.

120 3) Establishing ICCs will decrease transmission risk behaviors and HIV incidence among MSM
121 and PWID via improved access to prevention services (NSEP, OAT, IEC).

122

123 **METHODS/ DESIGN**

124 **Study design**

125 The study design is a cluster-randomized trial with parallel MSM and PWID strata. ICCs
126 were scaled-up and implemented at sites allocated to the intervention arm, and outcomes will be
127 assessed by pre- and post-intervention surveys at intervention and control sites (**Figure 1**). As
128 MSM and PWID are hidden populations with no sampling frame, respondent-driven sampling
129 (RDS) will be used to accrue samples for the two independent cross-sectional surveys. Sites (10
130 MSM and 12 PWID sites) were randomized in a 1:1 allocation ratio. The trial is currently
131 underway. The pre-intervention survey took place between September 2012 and December 2013;

132 the ICCs were scaled up between June 2014 and February 2015. Post-intervention survey
133 commenced in August 2016 and is expected to be complete by April 2017.

134 **Study sites**

135 Twenty-seven candidate sites were selected (15 PWID, 12 MSM; **Figure 2**) of which 22
136 were included in the trial. Sites were selected to represent regions of India where there was
137 preliminary evidence of high HIV prevalence or high risk of HIV acquisition through discussions
138 with the Targeted Interventions (TI) Division of NACO, India. We ensured sufficient distance
139 between sites to minimize potential overlap (contamination) between intervention and control
140 sites. MSM sites were selected to represent cities with established HIV epidemics among MSM,

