224 process is implemented in a systematic way that allows for the calculation of selection
225 probabilities. Participants select and provide referral coupons to individuals in their peer network
226 [50]. Verbal informed consent was obtained from all participants.

227 Eligibility criteria were:

- 228 1) ≥ 18 years of age
- 229 2) Present a valid RDS referral coupon
- 230 3) Be able to comprehend one of the languages in which the survey would be available
- 231 4) Male gender (MSM)
- 232 5) Oral or anal intercourse with another man in the prior year by self-report (MSM)
- 233 6) History of drug injection in the prior two years by self-report (PWID)

234 RDS was initiated at each site with participants (“seeds”) selected during ethnography.
235 Two seeds were selected from a list of 10 per site to represent varying demographic, geographic
236 (different parts of the city), HIV status, and for MSM sites, sexual identity (insertive vs.
237 penetrative vs. versatile) and for PWID sites, drug-related diversity (e.g., heroin vs. other opioid
238 injection; daily vs. less frequent injection) in the local population. While the initial plan was to
239 select 4-7 seeds, recruitment in nearly all sites proceeded at a rapid pace – therefore, in 25 of 27
240 sites no additional “seeds” were added. In one MSM and one PWID site, a third seed was added
241 as recruitment was slower than the other sites. In one PWID site (Moreh), recruitment was
242 terminated prematurely for safety considerations due to civil unrest.

243 “Seeds” and subsequent RDS recruits were asked to provide a scan of their fingerprint.
244 The fingerprint image is immediately converted to a unique hexadecimal code and stored; the
245 image itself is not stored. This code is linked to a study ID, which is used on participant forms

246 and laboratory samples and is also used to rule out duplicate enrollments within a site and to link
247 participation across multiple phases of the study.

248 All participants underwent a survey followed by HIV pre- and post-counseling and a
249 blood draw. Survey modules and laboratory tests are provided in **Table 2**. English language
250 versions of the surveys used at MSM and PWID sites are available as supplementary files. The
251 survey was conducted by trained interviewers who were hired expressly for the pre- or post-
252 intervention RDS surveys, did not work with or have previous interactions with the target

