Awareness of HIV status, access to care, and HIV treatment				
2	Awareness of HIV status among HIV-seropositive persons	1. Survey 2. Serologic HIV test	HIV seropositive participants	Reports having a positive HIV test OR being told by a doctor that he/she had HIV.
3	Accessing HIV medical care in prior 6 months	1. Survey 2. Serologic HIV test	HIV seropositive participants	Reports seeing a doctor about HIV AND reports visit with the indicated doctor in the prior 6 months.
4	Use of ART among ART-eligible	1. Survey 2. Serologic HIV test	HIV seropositive participants who meet either criteria 1 or 2 1. Reports taking ART at any time in the past OR 2. CD4 <350 cells/ μ L	Reports ART use in prior 30 days.
5	Use of trimethoprim-sulfamethoxazole (TMP-SMX) when indicated	1. Survey 2. Serologic HIV test 3. CD4	HIV seropositive AND CD4 count < 200 cells/ μ L	Reports taking TMP-SMX in past 30 days
6	Viral suppression among ART-eligible	1. Survey 2. Serologic HIV test 3. CD4 4. HIV RNA	HIV seropositive participants who meet either criteria 1 or 2 1. Reports taking ART at any time in the past OR 2. CD4 <350 cells/ μ L	HIV RNA <150c/mL
7	Viral suppression among HIV-positive	1. Serologic HIV test 2. HIV RNA	HIV seropositive participants	HIV RNA <150c/mL
8	Average CD4 cell count among HIV-positive	1. Serologic HIV test 2. CD4 cell count	HIV seropositive participants	CD4 cell count

Table 1. Outcome definitions for the Indian National Collaboration on AIDS (NCA) study

	Outcome	Data inputs	Population (denominator)	Definition
Risk behaviors, substance use, and depression				
9	Unprotected anal intercourse with non-main male partner in prior 6 months [MSM]	Survey	Participants at MSM sites	Does not report “always” using a condom during insertive or receptive anal sex with non-main (e.g., casual, one-time partner, sex worker) male partners in the prior 6 months
10	Number of non-main male sexual partners in prior 6 months [MSM]	Survey	Participants at MSM sites	Number of non-main male (e.g., casual, one-time partner, sex worker) male partners with whom the participant reports having insertive or receptive anal sex in the prior 6 months
11	Symptoms of sexually transmitted infection [MSM]	Survey	Participants at MSM sites	Reports genital/anal discharge, pain, or ulcer in prior 6 months
12	Syphilis infection	1. RPR test 2. TPHA test	Participants at MSM sites	Positive for syphilis infection by both RPR and TPHA tests

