13	Shared injection equipment in prior 6 months [PWID]	Survey	Participants at PWID sites	Reports sharing (passing or receiving) a needle and/or syringe with another individual in the prior 6 months
14	Shared injection equipment at last use among active injectors [PWID]	Survey	Participants at PWID sites that report injection of one or more drugs in prior 6 months	Reports sharing (passing or receiving) a needle and/or syringe with another individual at last injection
15	Reported injection abstinence in prior 6 months [PWID]	Survey	Participants at PWID sites	Denies injecting any drug in prior 6 months
16	Hazardous alcohol use or dependence	Survey	All participants	Score ≥ 8 (hazardous) or ≥ 15 on Alcohol Use Disorder Identification Test (AUDIT)[61]
17	Depression	Survey	All participants	Score ≥ 10 on Patient Health Questionnaire (PHQ)-9[62]

Table 1. Outcome definitions for the Indian National Collaboration on AIDS (NCA) study

	Outcome	Data inputs	Population (denominator)	Definition
Services and stigma				
18	Spouse HIV testing among married participants	Survey	Participants who report being married	Reports spouse has ever been tested for HIV
19	Symptoms of sexually transmitted infection for which participant sought care in prior 6 months [MSM]	Survey	Participants at MSM sites	Reports genital/anal discharge, pain, or ulcer in prior 6 months AND reports seeking medical care for symptom(s)
20	Used needle/syringe exchange program (NSEP) in prior 6 months [PWID]	Survey	Participants at PWID sites	Reports NSEP use in prior 6 months
21	Used needle/syringe exchange program (NSEP) in prior 6 months among active injectors [PWID]	Survey	Participants at PWID sites that report injection of one or more drugs in prior 6 months	Reports NSEP use in prior 6 months
22	Used opioid agonist therapy (OAT) in prior 6 months [PWID]	Survey	Participants at PWID sites	Reports OAT in prior 6 months
23	Stigma subtypes	Survey	All participants	Summed score from each of four 6-item stigma scales (enacted, vicarious, felt normative, and internalized stigma)[63]
Community viral load and HIV incidence				
24	Prevalence of viremic individuals in population	1. Serologic HIV test 2. HIV RNA	All participants	Prevalence of HIV-positive subjects with HIV RNA >150c/mL[64]
25	Average viral load in HIV-positive participants	1. Serologic HIV test 2. HIV RNA	HIV seropositive participants	Average (log ₁₀) HIV RNA

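### Table 1, outcome 9: read literally, the definition counts men with no non-main anal sex as having had unprotected anal intercourse

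*Combined protocol and SAP*

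**What the plan says.** Table 1 names outcome 9 "Unprotected anal intercourse with non-main male partner in prior 6 months". Its denominator is every participant at the MSM sites. Its event is "Does not report “always” using a condom during insertive or receptive anal sex with non-main" male partners in the prior 6 months. The row neither requires that such sex took place nor removes men who had none.

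Eligibility at MSM sites (Baseline pre-intervention assessment) is wider: "Oral or anal intercourse with another man in the prior year by self-report (MSM"). This admits men with oral sex only, with a main partner only, or with sex 6 to 12 months ago.

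Outcome 10 has the same denominator and counts "male partners with whom the participant reports having insertive or receptive anal sex in the prior 6 months". Zero is a possible value.

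Other rows of Table 1 deal with unexposed people explicitly:
- Outcome 13 needs a positive report: "Reports sharing (passing or receiving) a needle and/or syringe with another individual in the prior 6 months".
- Outcome 19 joins the underlying condition and the behaviour: "Reports genital/anal discharge, pain, or ulcer in prior 6 months AND reports seeking medical care for symptom(s").
- Outcomes 14 and 21 restrict the denominator: "Participants at PWID sites that report injection of one or more drugs in prior 6 months".

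Under Analysis plan, Community level, post-intervention cluster proportions are log-transformed and regressed on arm and on the log pre-intervention proportion, and the coefficient is exponentiated to a prevalence ratio.

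**The concern.** The name and the definition classify the same man in opposite ways. A man with no non-main anal sex in the window scores 0 on outcome 10, yet meets the outcome 9 event because he does not report 'always'. Outcome 9 uses none of the three safeguards found in outcomes 13, 14, 19 and 21.

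Hypothesis 3 states "Establishing ICCs will decrease transmission risk behaviors and HIV incidence among MSM" and PWID, and outcome 9 is the only MSM row in Table 1 that measures condom use. Under the literal rule, giving up non-main anal sex is never credited as reduced risk. A man who always used condoms and then stops such sex becomes an event; a man who did not always use them remains one.

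**Working it through.** **Plan's own figure.** The documents state no prevalence, effect size or power for outcome 9, so there is nothing to reproduce. The definition is checked by algebra, and every share below is an assumption.

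**Notation, for one arm.**
- a = share of MSM participants with no anal sex with a non-main male partner in the prior 6 months.
- c = share reporting 'always' among the rest.
- True prevalence, as the outcome is named: T = (1 − a)(1 − c).
- Prevalence as written, counting everyone except men with such sex who report 'always': W = 1 − (1 − a)c = T + a.

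The written rule therefore inflates prevalence by exactly a.

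**Effect on the ratio.** With 0 = control and 1 = intervention,

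W1/W0 = w(T1/T0) + (1 − w)(a1/a0), where w = T0/(T0 + a0).

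The recorded ratio lies between the true ratio and a1/a0. It is unbiased only if those two are equal or a = 0 in both arms. Ratios here are intervention over control. The plan codes its arm term for control, so its ratio is the reciprocal, and the pull toward 1 is the same.

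**Equal a in both arms; c = 50% control, 60% intervention.**

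| a | T0, T1 | True ratio | W0, W1 | Recorded ratio | Difference (true and recorded) |
|---|---|---|---|---|---|
| 10% | 0.45, 0.36 | 0.80 | 0.55, 0.46 | 0.84 | −9 points |
| 20% | 0.40, 0.32 | 0.80 | 0.60, 0.52 | 0.87 | −8 points |
| 30% | 0.35, 0.28 | 0.80 | 0.65, 0.58 | 0.89 | −7 points |
| 40% | 0.30, 0.24 | 0.80 | 0.70, 0.64 | 0.91 | −6 points |

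Check by the identity at a = 20%: w = 0.40/0.60 = 0.667, and 0.667 × 0.80 + 0.333 × 1 = 0.867.

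**If the intervention itself changes a.** These are crude post-intervention ratios with the same c values and an assumed 10-point gap, to show direction only.
- a = 20% control, 30% intervention: T 0.40 and 0.28, true ratio 0.70; W 0.60 and 0.58, recorded 0.97. The benefit is understated.
- a = 30% control, 20% intervention: T 0.35 and 0.32, true ratio 0.91; W 0.65 and 0.52, recorded 0.80. The benefit is exaggerated.

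**What the planned analyses absorb.** If a is stable over time in each cluster, W(post) − W(pre) = T(post) − T(pre). The pre/post-difference analysis that the plan says it will consider would then remove a, if run on the absolute scale. The log-baseline covariate would absorb part of a pre-existing difference in a between clusters. It does not undo the dilution in the table: with the same baseline in both arms, the arm coefficient is still log(W1/W0). Neither analysis removes a change in a caused by the intervention.

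**The case against.** The strongest reply is that the definition speaks of condom use during anal sex and so presupposes that the sex occurred. Rows of Table 1 are meant to be read across: outcome 11 takes its time window from the definition column, and outcome 12 takes its MSM restriction from the denominator column. Read with its name, outcome 9 would then require the act. That reading is available, and it is why the realised bias cannot be asserted. It does not settle the row. If the sex is presupposed, men without it must be either excluded or scored as non-events. Table 1 says neither, and the two choices give different estimands.

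A second reply is that the survey coding may handle this. That also stands as a possibility. The surveys are supplementary files that were not available here. The protocol mentions mandatory answers and programmed skip patterns but not how a skipped condom item is coded.

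Two stronger inferences are not supported:
- **That the trial would hide or reverse a benefit on this outcome.** That needs the intervention to shift a substantially, and no document figure supports a gap such as 10 points. Crude ratios also leave out the planned baseline adjustment.
- **That power is lost.** With equal a the absolute difference is unchanged. The rest depends on how a varies between clusters, which the documents do not give.

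Nor would it be right to say that no planned analysis bears on the problem, given the pre/post-difference analysis and the baseline term.

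**Conclusion.** The definition is wrong as written, of minor to moderate importance. Followed literally, it raises recorded prevalence by a and pulls the ratio toward 1 when a is equal between arms: from 0.80 to between 0.84 and 0.91 for a of 10 to 40%, under the assumed condom-use figures. If the intervention changes a, bias in either direction is possible.

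The fault in the wording rests on the text alone. The size of any realised bias does not, because neither a nor the coding rule is in the documents. The reach is limited to one of 25 secondary outcomes (numbers 2 to 26) at 10 of 22 sites. Outcomes 10 to 12 do not share the wording, and the primary outcome is untouched.

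**What to change.** Define the outcome 9 event as both of the following: the man reports at least one non-main male partner with insertive or receptive anal sex in the prior 6 months, and he reports condom use with such partners as less than 'always'. Score men with no such sex as non-events, keep all participants at MSM sites as the denominator, and state how a skipped condom item is coded.

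Apply the same coding to the pre- and post-intervention surveys, because the pre-intervention proportion is a covariate in the model. A version restricted to men with such sex may be added as supportive only, since the intervention can change who belongs to that group.

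The cost is one line of Table 1 and, if needed, a recode using the partner item that outcome 10 already requires. No new data are needed, and the primary outcome, sample size and randomization do not change. If the coding already works this way, correct the Table 1 wording alone.
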